#### Single/First treatment cycle

The safety and tolerability of a single treatment cycle of CLS12311 will be assessed in an ascending dose study across three dose groups involving a total of 9 patients. Patients will be allocated to a low (total dose [REDACTED]; n=2), medium (total dose [REDACTED]; n=3) or high dose (total dose [REDACTED]; n=4)

Each dose group will start with a sentinel patient, who will inform about the safety of the treatment before dosing additional patients. To ensure the safety of dosing in the subsequent patient, a minimum time interval of four days will be established prior to dosing the next patient. This time frame is based on preclinical data showing that peptide-coupled RBCs are fully processed in the first 24h after infusion (see IB 5.3). However, due to the individual manufacturing process of each product and related logistics, only one patient will start treatment per week. Patients who fail to meet the eligibility criteria during screening will be replaced.

The treatment will start with the lowest dose group (2 patients). Higher dose groups (medium dose in 3 patients, high dose in 4 patients) will only be initiated once safety data from the preceding dose group, based on (S)AEs and relapses, has been confirmed by Sponsor's medical

expert(s). The corresponding data should be entered into the eCRF in timely manner, within 24 hours at the latest.

The first patient in each dose group (sentinel patient) will receive a single treatment of CLS12311. Sentinel patients will not receive a second treatment cycle. All sentinel patients will be followed with safety visits until Visit 16 (week 48) according to the schedule of visit (see section 4.1). The safety follow-up of sentinel patients will inform about the safety of the treatment prior to second dosing of other patients.

### Second treatment cycle

The safety and tolerability of a second treatment cycle of CLS12311 will be evaluated in a subset of patients (n=6) from the single ascending dose study. Patients who receive a second treatment cycle in [REDACTED] of the trial will remain in the same dose group, i.e. low (total dose [REDACTED]; n=1), medium (total dose [REDACTED]; n=2) or high dose (total dose [REDACTED]; n=3). Hence, patients receiving a second treatment cycle will have the following total product exposure during the trial: low dose group [REDACTED] (n=1), medium dose group [REDACTED] (n=2) or high dose group [REDACTED] (n=3),

The [REDACTED] between the first and second treatment cycle is supported by preclinical safety studies of repeated dosing at monthly intervals over a period of three months. The safety of a [REDACTED] between autologous blood donations is also reflected in the dosing schedule.

The second treatment cycle will only be initiated after the safety of the first treatment cycle has been confirmed for the next higher dose group. The cumulative dose given to patients in the second treatment cycle will not exceed the dose of the first treatment cycle, which has already been administered to patients in the next higher dose group (see 5.2.3).

### Safety Monitoring and DSMB Review

Safety and tolerability will be assessed using vital sign measurements, clinical laboratory tests (hematology, blood chemistry, and urine tests), physical examinations, and monitoring for (S)AEs and relapses.

Twice, after patient 3 and then after patient 6 have completed [REDACTED], the Sponsor's medical expert(s) will review safety data, including any serious and severe events judged to be related to peptide-coupled RBCs, to confirm safety of repeated dosing for patient 2 and for patients 4 and 5, respectively.

To ensure availability of safety data a stringent enrollment of patients has been defined (Figure 7-1).

Patients 1, 2 and 3 will be enrolled to receive a dose of [REDACTED] of peptide-coupled RBCs (patients 1 and 2) or [REDACTED] (patient 3) in the first treatment cycle (see 10.2.1). Only after confirmation of the tolerability and safety of the first treatment cycle in **patient 3** (single dose of [REDACTED]) at safety assessments visit in [REDACTED], the second treatment cycle of patient 2 (total cumulative dose of [REDACTED]) will be permitted.

Accordingly, patients 4, 5 and 6 will be enrolled [REDACTED]. Patients 4 and 5 will only receive the second treatment cycle (total cumulative dose of [REDACTED]) if the [REDACTED] safety data of **patient 6** (single dose of [REDACTED]) will support second dosing of CLS12311.

The second treatment cycle of the last three patients (patients 7 - 9) will be administered only after the safety and tolerability of second treatment cycle has been confirmed in **patients 4 or 5**. If safety data of [REDACTED] from patients 3 or 6 are not available due to prematurely discontinuation, second dosing of patient 2, 4 or 5 need to be postponed until sentinel patients are replaced and safety data are available.

After the last patient in the high dose group has completed [REDACTED] safety data (including MRI data, relapses and EDSS) of all patients will be evaluated by the DSMB.

[figure not shown]

If any of the treatment regimens are deemed to be unsafe, the DSMB may recommend protocol modifications or omit any of the dose levels (see Section 19.1.3). A substantial change will be submitted for approval by IRBs/ECs and the regulatory authorities, in accordance with CTR and Swiss ClinO (see Section 19.7).

Dosing schedules and adherence to time frames (as mentioned above) between patients and across different sites and countries will be secured by close coordination between the Sponsor, the manufacturer and participating sites.

For patients who donated blood for study drug manufacturing and/or received at least one dose of study drug but prematurely discontinue treatment period and/or choose not to stay in the study until the [REDACTED], an Early Discontinuation (ED) visit will be performed (see section 14.1.9) to capture safety data and ensure continued patient monitoring.

**Figure 7-1    Patients’ enrollment and safety assessments in the treatment phase**

## 7.2 Safety Follow Up Phase: approx. 31 weeks

At the completion of the treatment phase, patients will enter a 31-week safety follow up (SFU) period, including three visits: three weeks after the end of the treatment period (Week 20), at Week 24 and at Week 48.

During the SFU, patients will be assessed at clinical visits as per Schedule of Events – please refer to Table 4.1 for further details.

The DSMB will reconvene after the completion of [REDACTED] to assess the safety outcomes of the trial.

[figure not shown]
If patients wish to discontinue the unblinded SFU and the last visit has been more than 8 weeks ago, they should be invited for an ED visit to capture safety data and ensure continued patient monitoring.

As the duration of the treatment effect is not known, patients may begin another DMT during the SFU, at the discretion of the investigator. However, every effort should be made to have patients complete the SFU and all related assessments, regardless of whether or not they receive alternative treatment for their MS.

In summary, this Phase Ib trial is designed to provide a maximum of safety throughout both single dose escalation and second treatment cycle.

Safety data will be evaluated by a DSMB after key milestones to assess the overall safety of CLS12311 and the different dose levels tested. A brief overview of the course of the Phase Ib study is shown in Figure 7-2.

## Figure 7-2 Study Design

## 8 STUDY POPULATION

### 8.1 Patient Population

The study population will consist of patients with a diagnosis of RRMS in accordance with the revised 2017 McDonald Criteria [5]. Given the gender and age distribution typical of MS - where females are affected up to three times more often than males - the study population is expected to reflect a higher proportion of female participants.

Patients previously treated with MS drugs will be allowed to participate in this study, provided that they did not take certain medications within the timeframes defined in the exclusion criteria.

It is mandatory that the decision for discontinuation prior treatments was made by the patient independently of the participation in the RED4MS trial. Patients entered for this study should not be withdrawn from MS therapies for the sole purpose of meeting eligibility for the RED4MS trial.

Screening and enrollment will focus on meeting the inclusion and exclusion criteria before performing the MRI and blood withdrawals required to assess the specific qualification/exclusion criteria.

Patients not eligible for the study will be considered as screening failures, i.e. no further study-related assessments/treatments will be performed on these patients and they will be offered the standard medical care by their physician.

To characterize the study population with respect to key HLA associations in MS, HLA typing for HLA- [REDACTED] alleles is performed. These alleles are among the most frequently associated with MS. [REDACTED]. The resulting data may be used for exploratory analyses.

#### 8.1.1 Inclusion Criteria

General inclusion criteria (to be assessed at the beginning of the baseline period based on patient interview and medical history):

- 1) RRMS according to the 2017 McDonald criteria
- 2) Male or female patients (assigned at birth) aged 18-55 years inclusive
- 3) Disease duration (since diagnosis) <10 years
- 4) EDSS at baseline 0-5.5
- 5) Untreated patients or patients being off therapy for the time-periods listed under exclusion criterion No. 2. Patients are either not eligible to receive approved therapies or have explicitly chosen not to receive such therapies after being adequately informed by the investigators
- 6) Only for female patients of childbearing potential (sexually mature, pre-menopausal and not surgically sterile): the patient is willing to use a highly effective method of contraception throughout the treatment phase or at least for 4 weeks after the last dose of the study drug. Accepted methods are:
  - Use of oral, injected or implanted hormonal methods of contraception or other forms of hormonal contraception that have comparable efficacy for example hormone vaginal ring or transdermal hormone contraception
  - Placement of an intrauterine device or hormone-releasing intrauterine system
  - Bilateral tubal occlusion or vasectomy of the male partner
- 7) Male patients willing to use contraception (such as a condoms) throughout the treatment phase or at least for 4 weeks after the last dose of the study drug, unless surgically sterile

- 8) Basic immunization against SARS-CoV-2, i.e. both doses of two-dose vaccines (or one dose of a vaccine and a SARS-CoV-2 infection before or after vaccination) OR a dose of a single-dose vaccine

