The second treatment cycle will only be administered after verifying the safety of the first treatment cycle given to the first patient in the next higher dose group, has been confirmed in [REDACTED]. Only after confirmation of the tolerability and safety of the treatment in **patient 3** (single dose of [REDACTED]) in [REDACTED], the second treatment cycle of patient 2 (total cumulative dose of [REDACTED]) will be permitted. Patients 4 and 5 will receive second treatment (total cumulative dose of [REDACTED]) only if the week 7 safety data of **patient 6** (single dose of [REDACTED]) will support a second dosing of CLS12311.

Information on the safety of the second treatment cycle in patient 2 will be available prior to administration of the second treatment in patients 4 and 5, as the information of the safety of the second treatment cycle in patient 4 or 5 will be available prior to dosing of the second treatment cycle in patients 7 - 9. In patients who received at least one dose of study drug and prematurely discontinue treatment period and/or choose not to stay in the study until the [REDACTED], a study visit according to the early discontinuation (ED) will be performed.

After the last patient in the high dose group has completed [REDACTED] the safety data (including MRI data, relapses and EDSS) from all patients will be evaluated by the DSMB.

**Safety Follow Up:** approximately 31 weeks

At the completion of the treatment phase at [REDACTED], patients will enter a safety follow up (SFU) of 31 weeks. During the safety follow up period patients will be assessed as per Schedule of Events - Table 4.1. Patients who discontinue the safety follow-up phase and their last visit has been more than 8 weeks ago, shall perform a study visit according to early discontinuation (ED) visit.

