Main inclusion criteria	
General inclusion criteria (to be assessed at the beginning of the baseline period based on patient interview and medical history):
 
 
1. RRMS according to the 2017 McDonald criteria
 
2. Male or female patients (assigned at birth) aged 18-55 years inclusive
 
3. Disease duration (since diagnosis) <10 years
 
4. EDSS at baseline 0-5.5
 
5. Untreated patients or patients being off therapy for the time periods listed under exclusion criterion No. 2. Patients are either not eligible to receive approved therapies or have explicitly chosen not to receive such therapies after being adequately informed by the investigators
 
6. Only for sexually active female patients of childbearing potential (sexually mature, pre-menopausal and not surgically sterile): the patient is willing to use a highly effective method of contraception (defined in the study protocol) throughout the complete treatment phase or at least for 4 weeks after the last dose of CLS12311
 
7. Male patients willing to use contraception (condoms) throughout the complete treatment phase or at least for 4 weeks after the last dose of CLS12311, unless surgically sterile
 
8. Basic immunization against SARS-CoV-2, i.e. both doses of two-dose vaccines (or one dose of a vaccine and a SARS-CoV-2 infection before or after vaccination) OR a dose of a single-dose vaccine
 

Main exclusion criteria	
General exclusion criteria (to be assessed at the beginning of the baseline period based on patient interview and medical history):
 
 
1. Patients with an active chronic disease (or stable but treated with immunomodulatory/-suppressive therapy) of the immune system other than MS (e.g. rheumatoid arthritis, scleroderma, Crohn's disease, ulcerative colitis, etc.) or with a known immunodeficiency syndrome (AIDS, hereditary immune deficiency, drug-induced immune deficiency)
 
2. Prior treatment with any of the medications below within the specified time-frame: 
 
a. glatiramer acetate, interferon-beta within 4 weeks prior to screening visit 1
 
b. dimethylfumarate, diroximel-fumarate within 4 weeks prior to screening visit 1
 
 
 

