### 10.2.4 Duration of Treatment

Patients of all three dose groups will receive treatment with CLS12311 within 13 weeks from enrollment in the study. CLS12311 will be administered at [REDACTED] for sentinel patients and at [REDACTED] for all other patients. CLS12311 will be manufactured from blood donations taken in [REDACTED] for treatments in [REDACTED] and from blood donation taken in [REDACTED] for treatments given [REDACTED]. Due to organizational reasons, the study design and the manufacturing schedule, the treatments may be postponed. However, both treatments of one cycle will be administered with an [REDACTED]. The sponsor and the manufacturer of the IMP will closely coordinate with the sites and other involved parties to organize all respective study visits, ensuring the adherence to the protocol. A minimum interval of [REDACTED] between the two blood donations will be maintained.

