#### **13.4.4 Risks of MRI**

Gadolinium is used as a contrast agent with MRI approved by the Swissmedic and European Medicines Agency (EMA). No serious side effects have been associated with its use. Approximately 5 to 10 percent of patients develop transient headaches following administration, but it is not clear whether the headaches are associated with the drug. The effect of gadolinium on the developing fetus remains partly unknown. Animal studies have shown a delay in development but no developmental abnormalities. Consequently, women of childbearing potential will be entered into this study only if an effective means of birth control is in use. A pregnancy test will be done prior to beginning the study and at each follow-up visit. The risk of nephrogenic systemic fibrosis is increased in patients with profoundly impaired renal function (glomerular filtration rate <30mL/minute).

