### 13.5 Pregnancies

Female patients should take all appropriate precautions to avoid becoming pregnant during this study. As such, women of childbearing potential should use adequate contraception throughout the trial, including the treatment phase and for 4 weeks after the last dose of CLS12311. Regular pregnancy tests will be performed during the study. Patients who become pregnant at any time during the study will be instructed to immediately inform the investigator and come in for an unscheduled visit. A positive pregnancy test must be confirmed by a urine pregnancy test at the central laboratory.

The Investigator has to document any pregnancy occurring in a female patient after the first study dose until patient's last study visit on the Pregnancy Report Form and submit to the Sponsor's designee immediately (i.e. no more than 24 hours after learning of the pregnancy), either by faxing or by emailing:

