Twice, after patient 3 and then after patient 6 have completed Visit █████, the Sponsor's medical expert(s) will review safety data, including any serious and severe events judged to be related to peptide-coupled RBCs to confirm safety of repeated dosing for patient 2 and for patients 4 and 5, respectively.

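### Criterion 6 lets contraception end earlier than section 13.5 asks of women, and a merely suspected pregnancy ends the remaining scheduled safety visits

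*Protocol*

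**What the plan says.** **Contraception period.** Criteria 6 (women) and 7 (men) in Protocol 8.1.1 ask for contraception "throughout the treatment phase or at least for 4 weeks after the last dose of the study drug". The synopsis (main inclusion criteria, Nos. 6 and 7) has the same structure: "throughout the complete treatment phase or at least for 4 weeks after the last dose of CLS12311". Section 13.5 says that women of childbearing potential "should use adequate contraception throughout the trial, including the treatment phase and for 4 weeks after the last dose of CLS12311". It sets no rule for men.

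**Population.** Synopsis No. 6 begins "Only for sexually active female patients of childbearing potential". Criterion 6 in 8.1.1 covers all women of childbearing potential.

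**Contrast agent.** Section 13.4.4 notes that gadolinium's effect on the fetus is partly unknown and concludes that "women of childbearing potential will be entered into this study only if an effective means of birth control is in use". It gives no end date. The end-of-treatment visit (14.1.5) includes a contrast MRI.

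**Pregnancy.** The synopsis withdrawal criteria require withdrawal from the study when pregnancy is detected at any time. The last sentence of 9.3.3 orders permanent study discontinuation for a suspected unplanned pregnancy, and only then mentions the confirming urine test. Section 13.5 describes an unscheduled visit and confirmation through the central laboratory. A dosed patient has an early discontinuation (ED) visit without MRI, and the pregnancy is followed to delivery.

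**The concern.** An entry criterion should not be looser than the safety section that governs the same behaviour. With *or*, meeting either limb is enough. A site working from criterion 6 and a site working from 13.5 could give women different end dates, and the two versions of criterion 6 cover different women. The product is first-in-human, and 13.4.5 says reproductive and developmental toxicity was not assessed in pre-clinical studies. The patients for whom the limbs differ most are the sentinels, who receive one cycle and then stay in follow-up with a contrast MRI still to come.

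The withdrawal rule raises a different issue. Section 14.5 already bars infusion in pregnancy, and 14.1.7 specifies follow-up MRIs without contrast. Ending the other visits adds no protection that stopping dosing and MRI would not give. It costs later adverse event and relapse data (primary endpoint) and EDSS data (secondary endpoint) in dose groups of 2, 3 and 4. Other dosed patients who stop treatment stay on the visit schedule (9.3.3), and those who start another disease-modifying therapy in follow-up are asked to complete it (7.2). The comparison has a limit: taking a prohibited therapy in the treatment phase does mean withdrawal.

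**Working it through.** The plan states no figure to reproduce. The check is text comparison and week arithmetic.

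**End of treatment.** Section 15.1 gives 17 + 31 = 48 weeks. Section 7.2 puts week 20 three weeks after the end of treatment: 20 − 3 = 17.

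**Two-cycle patients (6 of 9).** Section 10.2.4 says patients "will receive treatment with CLS12311 within 13 weeks from enrollment in the study". Latest last dose plus 4 weeks: 13 + 4 = 17. On schedule both limbs end together, so there is no gap before the end-of-treatment MRI.

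**Sentinels (patients 1, 3 and 6).**
- Patient 6: the synopsis allows the second cycle of patients 4 and 5 "only if the week 7 safety data of" patient 6, so that patient's single cycle ends before week 7. The shorter limb ends before 7 + 4 = week 11. Gap to week 17: more than 17 − 11 = 6 weeks.
- Patient 3: SAP 2.3.1 describes the reviews as "Twice, after patient 3 and then after patient 6 have completed Visit", with the visit number redacted. One visit is named for both patients, so the same bound follows, but by inference.
- Patient 1: the synopsis dosing table shows two placebo bags at week 3, so the last CLS12311 infusion is before week 3. The shorter limb ends before 3 + 4 = week 7. Gap: more than 17 − 7 = 10 weeks.
- Section 14.3 moves later visits by at least as much as any postponement, so the gaps to the visit do not shrink. The MRI itself may be done up to 5 days before the visit (14.1.5).

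**Pregnancy tests.** Table 12-1 excludes Visits 5, 6, 8, 12 and 14: 16 − 5 = 11 visits. Schedule footnote 20 excuses sentinels from two redacted visits without infusion. SAP 5.5.9 places infusion vital signs at Visits 3, 4, 10 and 11, so these are inferred to be Visits 10 and 11. That leaves 11 − 2 = 9 scheduled tests, with none between Visit 9 and the end-of-treatment visit.

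**Against 13.5, only if its whole-trial wording means week 48.** The longer limb ends 48 − 17 = 31 weeks earlier. The shorter limb for patients 3 and 6 ends at least 48 − 11 = 37 weeks earlier.

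**Data lost on withdrawal.**
- Detected at week 17: up to 48 − 17 = 31 weeks and three contacts (weeks 20, 24 and 48). Adverse events are assessed at all three; relapse and EDSS only at weeks 24 and 48.
- EDSS is scheduled at Visits 1, 7, 13, 15 and 16, so 2 of 4 post-baseline assessments are lost.
- Detected at week 24: 48 − 24 = 24 weeks and one visit.
- One patient is 1/2 = 50%, 1/3 = 33% or 1/4 = 25% of the low, medium or high dose group.

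**The case against.** Criterion 6 tests willingness at entry. Conduct is governed by 13.5, which already holds the stricter rule, and 13.4.4 puts no end date on birth control. A urine test is required at the end-of-treatment visit, or at the site before an earlier MRI. At most three patients are affected, and their sex is not stated. On pregnancy, the word *suspected* comes from one sentence that itself calls for a confirming test. Safety capture also continues: there is an ED visit with adverse event, relapse and EDSS assessment, pregnancy-related events are reported, and the pregnancy is followed to delivery. The secondary relapse endpoint covers only the treatment phase, so withdrawal in follow-up cannot affect it. Finally, SAP Final 2.0 (February 2026) followed a data review, which suggests that conduct was well advanced.

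Much of this stands and limits the size of the point. It does not remove the contradiction. Testing misses pregnancies too early to detect, and the visits after the ED visit are still lost.

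A reader might infer more than the documents support:
- *That women are left without a protective rule.* Section 13.5 supplies one. The consent form is not among the documents, so what patients were told is unknown.
- *That the criterion falls 31 or 37 weeks short.* This requires 13.5 to mean week 48. Its added mention of the treatment phase and 4 weeks would be superfluous on that reading, so it is not certain.
- *That *study drug* in 8.1.1 and CLS12311 elsewhere start different clocks.* The synopsis lists the study drug as CLS12311. Counting from placebo infusions would be a preference, and the documents give no reason for it.
- *That pregnancies are likely.* No rate is given.

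**Conclusion.** The point holds at moderate weight and should be corrected. Criterion 6, in both places, conflicts with 13.5 for women, and its two versions cover different populations. Read alone, it lets a sentinel of childbearing potential stop at least 6 weeks before the week-17 visit with the contrast MRI. That figure assumes a last infusion before week 7, which is documented for patient 6, inferred for patient 3 and exceeded for patient 1. The MRI concern does not apply to men; for them the issue is only the *or* in criterion 7.

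The pregnancy rule is a separate design choice. As written, 9.3.3 acts before confirmation. Together with the synopsis it gives up scheduled safety visits even after dosing is over, by at most 31 weeks and three contacts for a pregnancy found at week 17. No likelihood is attached to either part.

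**What to change.** - **Criterion 6 (8.1.1 and synopsis):** make it identical to 13.5, for all women of childbearing potential. State one end date in all three places, without shortening the 13.5 period.
- **Criterion 7 (both places):** require contraception for the treatment phase *and* for at least 4 weeks after the last dose of CLS12311, whichever is later.
- **9.3.3:** on a suspected pregnancy, hold dosing and MRI until the test result.
- **9.3.3 and synopsis:** on a confirmed pregnancy, stop dosing and MRI. With the patient's consent, continue the remaining non-MRI safety visits (adverse events, relapse, EDSS). This does not recover the imaging part of the primary endpoint.

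Cost: the entry criterion states a longer period for all women of childbearing potential, though 13.5 already asks for it. Male sentinels have a period at least 6 weeks longer than the shorter limb (at least 10 for patient 1). A consenting pregnant patient has extra visits. The change needs a protocol and consent amendment, with approval before implementation where subject safety is affected (19.7) and re-consent where willingness to take part may be affected (9.1).
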